Alcohol may also cause nausea in high doses; however, nausea is not expected at the dose being used in this sample of healthy volunteers who will report prior experience of consuming alcohol levels similar to the quantity used in this study. Alcohol dosing will be calculated using published gender specific algorithms based on estimated body water determined from height, weight, and age and the amount of alcohol provided will raise their blood alcohol levels to 80 mg/dl which is the legal limit of intoxication to levels.

Another area of potential risk to subjects under the influence of alcohol involves their safety during the experimental procedures. Although impairment of gross motor coordination in these subjects may occur, all subjects will be under the supervision of the experimenters to prevent possible accidents such as falls. To ensure the safety of our subjects, they will be monitored until their BAC falls to below .02 or until 6pm. All participants will be provided with transportation to and from the lab sessions to ensure their saftey.

There is no data looking at the effects of alcohol with mavoglurant. However, this interaction is the purpose of this study and the amount of alcohol that will be given subjects is no more than the amount they may drink in a social environment.

Risks associated with urine collections:

Screening urine collections are performed primarily as safeguards to subjects and should add no risks other than those normally associated with these procedures. Subjects will have approximately 50cc of blood drawn at the PE appointment to determine liver and kidney functioning. We will draw approximately 70.5cc of blood during the first lab session and 85.5cc of blood at the second lab session for BALs and health profile and PK samples. The morning after lab session 2, 50cc's of blood is drawn. At the 1 week follow up 50cc will be drawn again for health profile. Therefore, the total amount of blood drawn during the study (306 ml) is well within the HIC guidelines of 450 cc within 8 research weeks, and the blood loss poses minimal risk in healthy subjects. We will advise subjects against donating blood for 6 weeks following study participation.

BLOOD DRAW	PE	DS1	DS2	Morning after	1 WEEK F/U
Chem Profile (safety labs) 50 cc/draw	х	Х	Х	Х	Х
BAL (total 11 vials/visit) 0.5 cc/draw (5.5/DS)		Х	Х	Х	
PK Assay		Х	Х		
15 cc/draw			(2)		

Risks associated with rating scales and questionnaires:

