- d) SAFTEE: (Levine & Schooler, 1986) This is a standardized form for collecting side effects and adverse events. The SAFTEE includes 1) open-ended questions about any changes in physical or health problems, appearance, or activity level, and 2) yes/no responses to a specific list of symptoms (which correspond to anticipated side effects associated with NRT) for a specified time. For each symptom reported on the SAFTEE a rater also records the date of onset, severity (minimal, mild, moderate, severe), whether it was drug-related, and action taken. The SAFTEE is administered at baseline and daily during medication appointments and again before and after each alcohol challenge. We will monitor the number of patients experiencing symptoms and the severity of symptoms.
- e) Biphasic Alcohol Effects Scale (Martin et al., 1993) This 14-item self-report, unipolar adjective rating scale will be used to measure the stimulant and sedative effects of alcohol during the two lab sessions. This instrument has been found to be sensitive to naltrexone's effects on alcohol intoxication.
- f) Drug Effects Questionnaire -5 (Morean et al., 2013) The DEQ-5 asks the individual to report how they feel and_five items: FEEL a drug effect, feel HIGH, DISLIKE the effects, LIKE the effects, and want MORE of the drug (in this case alcohol). Each item is assessed with a separate, unipolar 100mm visual analog scale rated from "not at all" to "extremely".

- g) Blood Alcohol Levels: Blood samples will be drawn to measure plasma levels of blood alcohol concentration (BAC) during the two lab sessions. Blood samples will be spun at room temperature and the serum will be stored at -4°C. Sample will be defrosted and analyzed using a clinical alcohol analyzer from Analox Instruments that uses a rapid high-performance alcohol analysis procedure using alcohol oxidase.
- h) Health Profile and Urinalysis: Chemistry and CBC Panels will be drawn at baseline, prior to the lab sessions, the morning following the lab sessions, and at follow-up. Urinalysis will also be done at these times. Additionally, a pregnancy test for females will be done at intake and prior to both lab sessions.
- i) Psychophysiological Measures: will include heart rate and blood pressure. The cuff of the Dinamap will be on subject's dominant arm since the IV will be placed in the non-dominant arm.

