and pencil questionnaires about mood, medication and alcohol effects at regular time intervals, as well as the Body Sway Task.

At the end of the drinking session, the participant will be given lunch. They will be monitored for any remaining medication and alcohol effects. BAC levels will be taken every 30 minutes until the level falls to less than 0.02 (about 4 hours). Participants will be allowed to leave at approximately 6pm or when their BAC falls to below 0.02. All participants will be provided with transportation to and from lab session. The following morning participants will go to Quest for a blood draw and urine collection.

Follow Up Interviews

Subjects will receive phone calls on the two days following lab session 2 to see how they are doing and to assess any remaining side effects from the medication. Subjects will also participate in a 30-minute follow-up interview at one week after lab session 2. During this appointment, we will assess participants for any lingering side effects of the medication and obtain information about their drinking over the follow up period.

Payments for Participation (Economic Considerations)

Subjects will have the opportunity to receive up to \$630 for completing all parts of the study. Payment for the intake interview will be \$50. They will receive an additional \$65 for the physical examination/ in-person intake and up to \$20 for completing the MSDM task. Subjects will also receive \$140 for participating in the 1st laboratory session and \$200 for completing the 2nd laboratory session. Additionally, subjects will receive \$10 to take their study medication dose (7-10 days), for up to a total of \$100 and \$25 for the blood draw the morning after the second drinking session. Subjects will be paid \$30 for completing the one week follow-up appointment. If a subject is asked to come back in for a repeat lab appointment (blood work or EKG), he/she will be paid \$25. Subjects will be reimbursed for parking.

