9.3.1 Study Schedule

The study will consist of five parts: 1) Eligibility: Informed consent is obtained, and eligibility is evaluated, 2) Lab Session 1: Eligible subjects will be seen outpatient for Lab 1 where we will obtain baseline information and randomization to study medication. 3) Outpatient Medication: Subjects will be seen (virtually or in-person) on a daily basis, for 6-9 days, to take their study medication, 4) Lab Session 2: Subjects will again be seen outpatient for their second lab session. They will have their blood drawn and a urine collection the following morning. 5) Follow Up Interviews: We will follow up with participants via phone, for two days after lab session 2. They will be seen, one week after last session 2 for bloodwork, urine collection, and to assess for any potential remaining side-effects.

Phase/Day	Visits	Comments		
		Informed consent obtained prior to any study		
BL	Initial Intake Screening	procedures.		
		Includes vitals, blood, urine, EKG, and medical		
BL	Physical Exam	history.		
		Randomized to drug condition, vitals, blood, and		
Day 0	Lab Session #1	urine		
	Medication	1x/day staff observing subject administering		
Days 1-10*	Administration	medication.		
		Last dose of study medication, vitals, blood, and		
Day 7-10*	Lab Session #2	urine		
Day 8-11	Morning After LS 2	Blood and urine analysis		
FU	1 week Follow Up	Including final blood and urine analysis.		

*Medication taken for 7 to 10 days (pending schedule); Lab #2 occurs on day of last medication administration

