9.3.5 On Study Visits

Study Visit	Intake	Physcal Exam / In-Person Intake	Lab Session 1	Medication Administratio n (6-9 Days)	Lab Session 2	Morning After Lab Session 2	1 Week Follow-Up
Informed Consent	Х						
Health History	Х						
Alcohol Breathalyzer (not done for remote appointments)	Х		Х	X	Х		
CO level			Х		Х		
Eligibility Checklist	Х	X					
Randomization			X (before appt)				
Socio-demographic/General Info	Х						
Time to 1st Cigarette (Fagerstrom ND)	Х						
NIAAA alcohol questions on Alcohol Questions	Х						
SSADDA Risk/Protective Factors	Х						
Time to 1st Cigarette (Fagerstrom ND)	Х						
NIAAA alcohol questions	Х						
SSADDA Risk/Protective Factors	Х						
PROMIS Nicotine Dependence (ND)	Х						
EKG		X					
SCID (DSM-V) Summary and E section	X						
Time-Line Follow Back	X		Х	X	Х		X
SAFTEE			X	X	X		X
YCS	_		X		X		~
Biphasic Alcohol Effects Scale (BAES)	+		X		X		
Psychophysiological Measures	X	X	X	X	X		X**
Blood Alcohol Levels			X		X		
Plasma Mavoglurant Levels	+		X		X		
Menstrual Cycle Data	+	X					
QDRS	X						
Body Sway Task			Х		Х		
CPT	+		X		X		
SRT	_		X		X		
CRT	_		X		X		
AES	_		X		X		
Drug Test and Pregnancy Test (females)	X	Х	X	X*	X		
Blood Chemistry Panel and Urinalysis		X	X		X	X	X
Concomitant Medications	X		X	X	X		X
PROMIS Global Health		х					
Multi-Stage Decision Making Task (MSDM)		X					
Digits Backwards	+	X					
PROMIS Cognitive Function	+	X					
Barrett Impulsivity Scale (BIS-11)		^	Х				
Behavioral inhibition/activation system (BIS/BAS)		 	X				
		 	X				
UPPS Impulsive Behavior Scale (urgency subscales)	+	 	X				
Self-reported Habit Index (SRHI - Alcohol)			X				
PROMIS Sleep and Impairment Measures			X				
AUDIT-C * Drug and Pregnancy tests performed once during the the w	leek of medi	Lication administra					

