9.5 Planned Analyses

9.5.1 Primary Objective Analysis

Adverse events will be tabulated and rated for severity (mild, moderate, and severe) and for relation to the study intervention (unlikely, possibly, probably, and likely). Area under the curve will be measured for blood alcohol levels and compared between the two sessions (mavoglurant; baseline no-drug). Changes in serum chemistries, blood cell counts, and urinalysis will be compared before and after alcohol consumption between sessions (on drug, baseline no-drug). Quantitative outcomes will be analyzed using mixed models.

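### The between-session laboratory comparison in 9.5.1 needs an after-alcohol panel in Lab Session 1, which the schedule and session sheet do not provide

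*Combined protocol and SAP*

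**What the plan says.** The analysis, in 9.5.1: "Changes in serum chemistries, blood cell counts, and urinalysis will be compared before and after alcohol consumption between sessions (on drug, baseline no-drug". Quantitative outcomes are to go into mixed models, and 9.5.10 says these use all available data.

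The documents disagree on when the panels are taken:

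- 9.2(h): "Chemistry and CBC Panels will be drawn at baseline, prior to the lab sessions, the morning following the lab sessions, and at follow-up". The plural covers both sessions, and urinalysis follows the same times.
- 9.3.1, in the description of Lab Session 2 only: "They will have their blood drawn and a urine collection the following morning".
- 9.3.5: the row "Blood Chemistry Panel and Urinalysis" is marked at the physical exam, Lab Session 1, Lab Session 2, the morning after Lab Session 2 and the one-week visit. There is no column for a morning after Lab Session 1.
- 9.3, payments: $25 "for the blood draw the morning after the second drinking session", and no such payment after the first.
- 6.1.1: "We will draw approximately 70.5cc of blood during the first lab session and 85.5cc of blood at the second lab session", and then "The morning after lab session 2, 50cc's of blood is drawn".
- Section 11, procedure sheet: one Health Profile and one urinalysis, both at 11:00, with the first drink at 12:00.

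Two places are less definite. The narratives for both sessions in 9.3 describe a first set of labs at 11:00 and later mention safety labs without a time. Section 8.1 lists safety labs before drug, after drug and after alcohol, without naming the session.

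**The concern.** A comparison of before-to-after changes between two sessions needs four cells: before and after alcohol, in each session. If no panel follows alcohol in Lab Session 1, one cell is empty by design for everyone. A mixed model can use incomplete records, but it cannot supply a cell that nobody contributes to.

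Section 8.2 names blood counts and serum chemistries as primary outcomes, and Specific Aim 1 concerns their values before and after alcohol. The sentence in 9.5.1 is the only planned comparison of those values. Under 9.2.1 an abnormal result may be recorded as an adverse event and so be tabulated, but a tabulation does not estimate change. The 11:00 panel in Lab Session 2 cannot stand in for the missing cell, because it follows 7-10 days of study medication.

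**Working it through.** **Which session the sheet describes.** Only one sheet is visible. It hands out medication ahead of a first dose the next day, includes questionnaires that 9.3.5 marks at Lab Session 1 only, and takes one mavoglurant sample, which is the Session 1 number in 6.1.1 and 9.2.2. It is therefore the Session 1 sheet, and Session 1 is where the missing cell lies.

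**Blood volumes (6.1.1: 50 cc per panel, 11 alcohol samples of 0.5 cc per session, 15 cc per mavoglurant sample).**

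- Session 1: 50 + 11 × 0.5 + 15 = 70.5 cc, as stated, so one panel.
- Session 2: 50 + 11 × 0.5 + 2 × 15 = 85.5 cc, as stated, so one panel.
- Total: 50 + 70.5 + 85.5 + 50 + 50 = 306 ml, as stated, with one morning-after panel.
- With a morning-after draw for Session 1: 306 + 50 = 356 ml.
- With a second in-session panel in both sessions instead: 306 + 2 × 50 = 406 ml.

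Both alternatives stay below the stated limit of 450 cc. The 50 cc is nominal: the tubes on the sheet hold 2 × 5 + 4 = 14 ml. The 6.1.1 table also marks a morning-after alcohol sample that the 306 ml leaves out. The volumes show how many panels the risk section counts, not what was drawn.

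**Payments (9.3).** 50 + 65 + 20 + 140 + 200 + 100 + 25 + 30 = $630, the stated maximum, with a single $25 morning-after draw.

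**Estimability.** Code session s (0 = Session 1, 1 = Session 2) and time t (0 = before, 1 = after alcohol), with columns intercept, s, t and s×t. Under the schedule and sheet the observed rows are:

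- Session 1 before: 1, 0, 0, 0
- Session 2 before: 1, 1, 0, 0
- Session 2 after: 1, 1, 1, 1

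The rank is 3 for 4 parameters. A contrast is estimable only if appending it leaves the rank unchanged. Appending session × time (0, 0, 0, 1) raises the rank to 4, so it is not estimable.

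Adding arm and all its interactions gives 6 rows, 8 parameters and rank 6. Session × time and arm × session × time both remain not estimable. Two contrasts are estimable: the arm difference in the Session 2 change, and the arm difference in the change between the two 11:00 panels. If 9.2(h) governs instead, the rank is 4 of 4 (8 of 8 with arm) and every contrast is estimable.

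**Precision of the estimable replacement.** For the Session 2 change adjusted for one covariate, the expected 95% half-width in residual SDs is

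t(0.975, N − 3) × √(1/n₁ + 1/n₂ + d²/(N − 2)),

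where d is the arm difference on the covariate in SDs. The planned size is 14 v 14. Section 7.2 implies 10 + 14 = 24 completers so far, and their split by arm is assumed.

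| Arms | d = 0 | d = 0.5 |
|---|---|---|
| 14 v 14 (25 df) | 0.778 | 0.804 |
| 12 v 12 (21 df) | 0.849 | 0.877 |
| 10 v 14 (21 df) | 0.861 | 0.889 |

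**The case against.** The best counter-argument is that a post-alcohol panel may exist in Session 1. The Session 1 narrative has a first set of labs at 11:00 and then untimed safety labs, and 8.1 mentions labs after alcohol. This remains possible, which is why the conclusion is conditional. But a panel of that kind is missing from a sheet timed to the quarter hour and is not counted in the 70.5 cc. The three times in 8.1 also fit the three-cell schedule: 11:00 in Session 1, 11:00 in Session 2, and the morning after Session 2.

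A second argument is that the sentence in 9.5.1 is loosely worded and could mean two separate comparisons, before v after alcohol and drug v no drug, each estimable from three cells. However, its subject is changes compared between sessions, and 9.5.3 uses the same construction for changes after alcohol in the exploratory measures. The change-by-session reading is the natural one.

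Third, this is an exploratory pilot with no power calculation, and adverse events, heart rate, blood pressure and blood alcohol AUC do not depend on the missing panel. That limits the damage. It does not rescue the laboratory comparison, because no sample size fills an empty cell.

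One caution stands. In Session 2 the last dose is at 8:15, so the 11:00 panel comes under three hours after it and the next-morning panel roughly a day after. The change in Session 2 therefore mixes any drug-alcohol interaction with time since the last dose. This applies equally to the planned contrast and to the replacement, and it should be stated when either is reported.

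**Conclusion.** The concern holds. The sections contradict each other on whether an after-alcohol panel follows Lab Session 1. If the schedule and session sheet govern, the only planned comparison of the primary laboratory values cannot be estimated: 3 of 4 cells, or 6 of 8 with arm in the model. The contradiction is certain. The loss of the analysis depends on which version was followed, which the documents do not show, and on reading 9.5.1 as change by session. The effect is confined to chemistries, blood counts and urinalysis. The randomised comparison that remains has an expected half-width of about 0.8 to 0.9 residual SD, assuming complete data and an arm difference of no more than 0.5 SD on the covariate.

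**What to change.** 1. Establish from the records which panels were drawn. Staff without the randomisation list should do this, without looking at results by arm; under 9.1.4 the biostatisticians hold the blinding information. Then reconcile 6.1.1, 8.1, 9.2(h), 9.3, 9.3.1, 9.3.5 and the sheet with 9.5.1.
2. If no after-alcohol Session 1 panel exists, amend 9.5.1 before laboratory data are seen by arm.
   - Compare mavoglurant with placebo on the change from the 11:00 Session 2 panel to the next-morning panel, adjusted for the pre-drug 11:00 Session 1 value. In the mixed model this is arm × time on the two Session 2 panels, with the Session 1 value and its interaction with time as covariates. With complete data it gives the same estimate as ANCOVA of the change (0.3226 both ways on simulated data).
   - Keep adjustment for the on-drug 11:00 Session 2 value as a sensitivity analysis only.
   - Report the drug effect before alcohol as the 11:00 Session 2 value by arm, adjusted for the 11:00 Session 1 value.
   - Tabulate non-numeric urinalysis results by arm at the same times.
3. If Session 1 after-alcohol panels were drawn, keep the contrast, state when they were taken, and correct the schedule, visit table, payments and blood total.

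The cost is a record check and an amendment with IRB approval (10.2) and notice to the sponsor and FDA (10.13). No extra draw or visit is needed. The replacement gives up the within-person drug v no-drug comparison and has the wide intervals shown above. It also changes a primary-outcome analysis after about 24 completers, with mavoglurant levels from 10 already analysed. The amendment should state that laboratory data had not been seen by arm or, if they had, label the replacement post hoc.

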The study will consist of five parts: 1) Eligibility: Informed consent is obtained, and eligibility is evaluated, 2) Lab Session 1: Eligible subjects will then be exposed to a fixed dose of alcohol and monitor responses; we will randomize them to study medication (mavoglurant or placebo), 3) Outpatient Medication: Subjects will come in on a daily basis (or via zoom) for 7-10 days, when they will be observed when they take the study medication, and adverse events will be monitored, 4) Lab Session 2: Subjects will again be exposed to the same fixed alcohol dose at the first lab session, the following morning they will go in for a blood/urine collection 5) Follow Up Interviews: We will follow up with participants via phone, for two days after discharge and in-person, one week after discharge to assess for any potential remaining adverse events.

Number of Study Sites

This is a single site study

Study Population

40 social drinkers who are not currently seeking treatment for their drinking behavior, and who are willing to abstain from drinking alcohol during the study, and who are between 21-50 years of age.

Number of Participants

40 social drinkers will be recruited to achieve 28 completers.

Primary Outcome Variables

To evaluate the effect of mavoglurant on blood chemistries, urine toxicology and physiological safety measures before and after alcohol administration.

Secondary and Exploratory Outcome Variables (if applicable)

To evaluate the interactions of alcohol and mavoglurant on blood alcohol levels and mavoglurant levels.

APPROVED BY THE YALE UNIVERSITY IRB 11/22/2023

2000021703 Version 2.9

To explore the effects of mavoglurant on alcohol responses, including stimulation, sedation, intoxication, and cognitive/motor performance.

2 Abbreviations

Abbreviation	Explanation				
ADP	Alcohol Drinking Paradigm				
HRU	Hospital Research Unit				
СМНС	Connecticut Mental Health Center				
AUD	Alcohol Use Disorder				
CTNA	Center for Translational Neuroscience on Alcoholism				
AE	adverse event				
ALT	alanine aminotransferase				
AST	aspartate aminotransferase				
BAC	blood alcohol concentration				
CLIA	Clinical Laboratory Improvement Act				
CIWA-AR	Clinical Institute Withdrawal Assessment for Alcohol-revised				
DSM-5	Diagnostic and Statistical Manual of Mental Disorders – Fifth Edition				
DSMB	Data and Safety Monitoring Board				
EKG/ECG	electrocardiogram				
EtOH	ethanol				
FDA	Food and Drug Administration				
GGT	gamma-glutamyl transferase				

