8.1 General Design Description

Double blind placebo-controlled trial of mavoglurant vs. placebo in light social drinkers (i.e., consuming 1- 6 standard alcoholic drinks per week and having engaged in at least one and no more than 12 binge drinking episodes in the past year). Participants will not meet criteria for a DSM-V Alcohol Use Disorder and must be willing to abstain from alcohol during the outpatient medication treatment phase. We propose to recruit 40 male and female social drinkers (to achieve a completer sample of 28 participants).

Subjects will sign informed consent and eligibility will be determined. Eligible subjects will participate in two alcohol administration lab sessions. They will be randomized to receive either 200 mg/day of mavoglurant or placebo for 7-10 days (14 in each study arm). During the outpatient medication administration phase, subjects will be observed daily as their medication is administered. Adverse events will be assessed. The first lab session will occur on Day 0 (prior to start of study medication) and the second lab session will occur following 7-10 days (as scheduling permits) of study medication. During each lab session, subjects will receive six successive doses of alcohol over a 90-min period designed to raise their blood alcohol levels to 80 mg/dl. Outcomes will include adverse events (during outpatient period and the lab session), safety labs (before and after drug and after alcohol), PK/PD of drug and alcohol, behavioral tests of cognition and body sway as well as self-reports of intoxication and other alcohol effects. Study staff will check in with subjects on the two days following the second lab session and an in-person follow up appointment will be scheduled 1 week after the second lab session.

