- 10) Subjects who have taken any investigational drug and/or participated in another study which involves additive blood sampling and/or interventional measures that would be considered excessive in combination with the current protocol within 4 weeks immediately preceding admission to the treatment period.

APPROVED BY THE YALE UNIVERSITY IRB 11/22/2023

2000021703 Version 2.9

- 11) Subjects who report any daily drug use during the 30 days prior to randomization for the following: anxiolytics, beta blockers, central nervous system stimulants, hypnotics, non-therapeutic doses of neuroleptics and antidepressants, drugs with psychotropic activity or drugs which cause excessive sedation.
- 12) Subjects who have donated blood within the past six weeks.
- 13) Current use (within 30 days of screening) of specific psychoactive medications (e.g., typical neuroleptics, narcotic analgesics, antiparkinsonian medications, systemic corticosteroids, or medications with significant central anticholinergic activity, etc.)
- 14) Current use of warfarin.
- 15) Use of any medications that are contraindicated with mavoglurant and alcohol.
- 16) AST, ALT, total bilirubin >1.5 times upper normal; serum creatinine, >2 times upper normal limit, total bilirubin>1.5 times ULN; Serum creatinine >2.0 times ULN.

9 Methods

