9.4 Statistical Method

9.4.1 Statistical Design

This study is exploratory in nature and seeks to determine effect sizes to be used in subsequent years, in the larger-scale studies, and to determine if alcohol and mavoglurant can be safety used together. Therefore, no formal power calculations have been performed. The design employed here, including the chosen sample size, are relatively standard in pilot studies (Galasko et al., 1997; Sinha, et al., 1999)

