9.4.2 Sample Size Considerations

As noted above, due to the exploratory nature of this pilot study, the chosen sample size is relatively standard in pilot studies.

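### The primary laboratory analysis models changes between sessions and plans no per-person summary, so a large rise in one to three of the 14 people on drug would not stand out

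*Combined protocol and SAP*

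**What the plan says.** Section 7.1 makes safety and tolerability of mavoglurant with alcohol the primary objective. Section 8.2 names blood counts, chemistries and liver function tests among the primary outcomes.

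Section 9.5.1 gives their analysis: "Changes in serum chemistries, blood cell counts, and urinalysis will be compared before and after alcohol consumption between sessions", the two sessions being the on-drug session and the no-drug baseline session. It adds: "Quantitative outcomes will be analyzed using mixed models". How the placebo arm enters is not stated. The same section also tabulates adverse events by severity and by relation to the intervention. Section 9.5.4 (Safety) is marked not applicable because safety is already the main object. No section plans a count of participants beyond a limit, a shift table, a worst-value summary or a laboratory listing.

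The blood-draw table in Section 6.1.1 shows five safety panels per person: physical exam, Session 1, Session 2, the morning after Session 2, and the 1-week follow-up. Section 9.3.1 describes the last visit as "Including final blood and urine analysis".

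The design is "14 in each study arm" (Section 8.1). On power, Section 9.4.1 says: "Therefore, no formal power calculations have been performed". No significance level is given. The only numeric laboratory limits are in an exclusion criterion (Section 8.3.2): "AST, ALT, total bilirubin >1.5 times upper normal; serum creatinine, >2 times upper normal limit".

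**The concern.** In a study this small, organ toxicity from the drug or from the drug with alcohol is likely to appear as one or two people with large rises, not as a shift of the whole arm. A mixed model of changes ordinarily estimates average change, and an extreme individual inflates the standard deviation along with the mean. The primary laboratory analysis is therefore weakest for the pattern a first drug-alcohol safety study most needs to see. Section 6.1 places this trial ahead of a study in heavy drinkers, and Section 6.1.1 says no data exist on the combination.

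The comparison is also confined to the two sessions, so an abnormality first seen at 1 week appears to have no place in any laboratory analysis.

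**Working it through.** **Inputs.** 14 completers per arm (Section 8.1). Assumed, because the protocol gives none: a two-sided 5% level, and shift sizes in units of the SD of the change score. T-tests stand in for the mixed-model contrast, whose form is not specified.

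**The plan's own figure.** There is no power calculation to reproduce. The counts agree: 2 × 14 = 28, and 28 of 40 recruited implies 30% attrition (1 − 28/40).

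**Limiting t statistic.** Let *k* of *n* people rise by *D* and the rest not change. The mean change is *kD/n*, and its standard error is (*D/n*)·√[*k*(*n*−*k*)/(*n*−1)]. *D* cancels:

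t = √[*k*(*n*−1)/(*n*−*k*)]

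The same value results within the 14 on drug (paired; 13 df; critical value 2.16) and for 14 against 14 unchanged placebo participants (26 df; critical value 2.06).

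| Affected of 14 | t |
|---|---|
| 1 | √(13/13) = 1.00 |
| 2 | √(26/12) = 1.47 |
| 3 | √(39/11) = 1.88 |
| 4 | √(52/10) = 2.28 |

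Four affected is the first count that can pass either critical value in this limit.

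**With background variation.** Chance of a significant increase in 100,000 simulated trials, shown as 14 v 14 / paired. With nobody affected it is about 2.5%.

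| Affected | 3 SD | 5 SD | 10 SD | 20 SD |
|---|---|---|---|---|
| 1 | 4.5% / 4.2% | 3.9% / 2.5% | 1.0% / 0.1% | 0.0% / 0.0% |
| 2 | 8.7% / 8.6% | 8.9% / 6.3% | 4.1% / 0.9% | 0.1% / 0.0% |
| 3 | 16.2% / 17.6% | 21.0% / 18.4% | 21.6% / 11.0% | 13.2% / 1.7% |

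For one person the chance falls as the rise becomes more extreme.

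**The adverse-event route.** Section 9.2.1 mentions abnormal laboratory results in its causality definitions. It sets no threshold at which a value becomes an adverse event, and the grading scale is still a template placeholder. The fallback severity definitions turn on treatment needed and interference with daily life, which does not grade a symptomless laboratory rise.

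**Can the planned contrast be formed?** Section 9.2(h) puts panels on the morning after the lab sessions, in the plural. Sections 9.3.1 and 9.3.5 show a morning-after draw only for Session 2. The appendix draws the health profile at 11:00, an hour before the first drink. The volumes in Section 6.1.1 fit one 50 cc panel per session:

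- Session 1: 50 + 5.5 + 15 = 70.5.
- Session 2: 50 + 5.5 + 2 × 15 = 85.5.
- Total: 50 + 70.5 + 85.5 + 50 + 50 = 306, the protocol's own figure.

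Section 9.3 mentions safety labs again after describing the drinks, but gives no time for a second panel. On this schedule Session 1 has no post-alcohol panel, so its before/after change cannot be computed.

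**What a per-person count shows.** One case in 14 is 7.1% (exact 95% CI 0.2% to 33.9%). None in 14 has an upper limit of 1 − 0.025^(1/14) = 23.2%. At assumed true rates of 5% and 10%, the chance of seeing at least one case is 1 − 0.95^14 = 51% and 1 − 0.90^14 = 77%.

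**The case against.** Several points on the other side have force.

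- **The adverse-event table is part of the same primary analysis.** The investigator reviews adverse events after each completed subject (Section 9.2.1), and the DSMB sees safety reports twice a year (Section 10.12). A reader might infer that a severe liver or renal abnormality would leave the trial reporting no laboratory effect. The documents do not support that, because the case could be recorded as an adverse event. What stands is that this depends on someone's unguided judgement.
- **No testing rule is stated.** The study is exploratory and aims at effect sizes (Section 9.4.1), so the critical values are only a yardstick. A reader might also infer a count of false positives across analytes. Neither the number of tests nor their level is given, so no such figure can be derived.
- **The model is unspecified.** The word mean does not appear in Section 9.5.1; it is inferred from changes analysed by mixed models. The t values apply to the two readings above. A within-drug contrast using a variance pooled with an unchanged placebo arm would multiply them by √2, giving 1.41 for one person and 2.08 for two. One case would still fall short of 2.06, and two would be borderline.
- **The 1-week panel is not expressly excluded.** Section 9.5.1 does not define which draws count as after alcohol, and Section 8.1 lists safety labs broadly as outcomes. Exclusion is the ordinary reading of a between-session contrast, but it is not stated. The missing-data sentence in Section 9.5.10 names no time points and settles nothing.
- **Counts have no more testing power.** Fisher's exact test gives p = 1.00 for 1 v 0 and 0.48 for 2 v 0, and first falls below 0.05 at 5 v 0 (p = 0.041). The gain is in display, so the remedy must be descriptive.

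**Conclusion.** The concern holds as a gap in the primary laboratory analysis. Under the paired or 14 v 14 reading and an assumed 5% level, a large rise in one, two or three of 14 gives a limiting t of 1.00, 1.47 or 1.88, below 2.16 and 2.06. With background noise, the simulated chance of a significant increase is at most 4.5% for one person and 8.9% for two, over assumed shifts of 3 to 20 SD. Individual toxicity would then show only through an adverse-event tabulation that has no laboratory trigger and no completed grading scale. On the ordinary reading, the 1-week panel is unused in the laboratory analysis.

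The finding does not show that toxicity would go unreported. It shows that the plan does not ensure it would be displayed. Separately, the planned between-session change may not be computable until the panel schedule is reconciled.

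**What to change.** In Section 9.5.1:

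1. Make the lead laboratory summary descriptive. By arm, count participants whose worst value after the first dose (Session 2 before alcohol, the morning after, 1 week) exceeds a pre-specified reporting limit. The limits in Section 8.3.2 can serve as reporting thresholds only, not as clinical rules.
2. For other analytes, count shifts from inside to outside the reference range.
3. Give exact 95% confidence intervals and a listing of each person's five panels, with no reliance on significance tests. Use as denominator everyone dosed who has at least one later panel.
4. Reconcile Section 9.2(h) with Sections 6.1.1, 9.3.1, 9.3.5 and the appendix on whether a post-alcohol panel exists for Session 1. Keep the mixed models as supportive only after that.

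The cost is some added wording, one table and one listing. The descriptive summary needs no new samples, because every panel it uses is already scheduled.
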